Human Subjects Involvement and Characteristics. We will recruit 40 subjects for this study who are overweight or obesity class 1. Subjects will be required to meet the following inclusion criteria: 1) Hispanic/Latino men aged 35-55 years; 2) BMI $\geq 27 \text{ kg/m}^2$; 3) CDC pre-diabetes risk score ≥ 9 ; 4) not currently engaged in soccer practice or other PA or lifestyle intervention program; 5) ability to read in English or Spanish and provide informed consent; Exclusion criteria are participants with 1) T2DM diagnosis or medication; 2) BMI ≥ 33 ; 3) resting blood pressure $\geq 165/100$ at screening 4) any mobility issues or contraindications for HIIT PA program. Subjects will be recruited from local Atlanta area Latino health centers. Each subject will receive a free intervention performed by trained soccer coaches in a small group format. Enrollment fees for league play will be covered by the study. Retention of these subjects will be aided by text messages given through the app technology used to track physical activity. **Research Material Collected:** These will include medical history (previous diagnoses), demographic information, anthropometrics, blood pressure, HbA1c, physical activity assessments and tracking of physical activity via a fitness tracker throughout the study.

Potential Risks:

There is some mild discomfort with the finger stick required by the HbA1c point-of-care device. Standard sterile techniques will be used; thus, infection is unlikely. There is small-to-moderate risk of injury with the most common being muscle strains and joint sprains while playing soccer and during conditioning. However, we will implement an evidence-based approach proven to reduce in up to 40% the risk of common soccer injuries and protocols to screen for exercise-related adverse events. Soccer coaches will be certified in cardio-pulmonary resuscitation and soccer field protocols for emergency situations reviewed and improved as needed, including availability of AED's. There is a small risk of loss of confidentiality. We will follow all procedures required by Emory University to protect participants. Efforts will be made to ensure that all personal information remains confidential. All data will be stored in locked offices and password-protected computers. The study app we will be using is HIPAA compliant and approved by Emory IT services. Personal identity will be protected in any publication.

Adequacy of Protection Against Risks

Recruitment and Informed Consent: Aim 2 will require prospective recruitment of 70 (expect 30 screen fails for an enrollment of 40) subjects. Recruitment will be through Latino health centers. Permission to perform this study will be sought from the Emory University IRB. At the time of screening, the trained study staff will discuss the study with the subject and give them all the information listed above in language understandable at the level of the subject and all information needed to make an informed choice about participation. Informed consents will be obtained prior to initiating any study procedure.

Protection Against Risk: Risk will be minimized to the subjects by continuous monitoring and water breaks when needed. Risk to confidentiality will be reduced by using non-identifying participant numbers and removing all identifiers as early as feasible. Only study personnel will have access to identifying data. Coaches will be on a first name basis with subjects but not have access to non-relevant data.

Potential Benefits of the Proposed Research to the Participants and Others

The proposed research has substantial potential benefits for these men. The positive engagement of Hispanic men in a successful diabetes prevention program will allow for expansion into other communities as well as with children and adolescents and women, ultimately resulting in improved quality of life in the Hispanic community. Each man in the study will undergo assessments not typically clinically available.

Any new diagnosis of diabetes or potential hypertension that occurs during the research studies will be shared with the subject and they will be referred to their doctor or health clinic.

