Subject population: Hispanic overweight males age 35 to 55 years with a CDC pre-diabetes risk score ≥ 9 and not currently engaged in soccer or other regular physical activity.

Specific Aims

We will test the following central hypothesis: **A soccer-based adaptation to the DPP can be feasibly implemented in a population of middle-age Latino men at high risk for T2DM.**

Aim 1: *1a:* To adapt the current National Diabetes Prevention Program (NDPP) curriculum to a novel, translational soccer-based DPP programming and delivered by trained coaches as facilitators.

1b: To conduct formative research addressing barriers and acceptability for implementation of this soccer-based DPP adaptation among Latino adults via questionnaires and key informant interviews.

Aim 2: *2a:* To assess implementation feasibility of this novel soccer-based DPP adaptation by conducting a single-arm, pre-post pilot study among Latino males (n=40; 35-55 years) residing in the Atlanta metro area.

2b: To explore preliminary signals for improvements in objectively-measured PA, dietary behaviors, physical fitness and body composition outcomes with our soccer-based DPP adaptation.

Overweight (BMI between 25 and 60 kg/m²) participants at high risk for T2DM (CDC pre-diabetes screening tool score >9)(25) will be recruited through soccer interest groups, local leagues and Hispanic health organizations. After a baseline assessment visit, participants will attend soccer practice twice/week for 12-weeks while completing NDPP core curriculum modules with facilitated discussion by trained coaches during each soccer practice. Participants will then be invited to join an established small-sided soccer league in their community (12-weeks) offering one game/week and also complete the NDPP maintenance modules and PA/diet self-tracking via mobile health technologies. After the core (12-weeks) and maintenance intervention periods (24- weeks) baseline measurements will be repeated. We will also conduct a 1-year follow up assessment after 6 months of minimal contact. Data on the feasibility of this DPP soccer-based adaptation will inform future randomized, controlled trials testing the effectiveness of this translation model to reduce T2DM risk while extrapolating to other sports-based adaptation and age, gender and racial sub-populations.

Research Design:

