- 3) CDC pre-diabetes risk score ≥ 9 (25)
- 4) Not currently engaged in soccer practice or league or other PA or lifestyle intervention program
- 5) Ability to read in English or Spanish and provide informed consent

Exclusion criteria

- 1) T2DM diagnosis or medication
- 2) BMI ≥ 41
- 3) Resting blood pressure $\geq 165/100$ at screening
- 4) Any mobility issues or contraindications for HIIT PA program (26)

Recruitment: Participants will be recruited from the mentioned local Atlanta area organizations using online a study recruitment flier in both print and electronic format. Interested participants will be provided an online survey to ascertain eligibility (CDC pre-diabetes screening, demographic questions and PA habits) and those meeting inclusion criteria will be invited to an informative session at one of participating soccer field for informed consent and confirmatory baseline assessments including BMI, blood pressure, HbA1c and exercise pre-participation risk screening. Siemens DCA Vantage HbA1c point-of-care devices will be used for screening of diabetes. (27) A cut off point of 6.5% will be used as a putative definition of diabetes and these individuals will be referred to a local clinic for confirmatory testing and appropriate management. (28) Both systolic and diastolic blood pressure will be measured while sitting using a calibrated electronic blood pressure sphygmomanometer prior to any activity and after five minutes of rest. Participants meeting inclusion and exclusion criteria will be invited to participate in the study.

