Data and statistics will be managed by the PI and the study team using RedCap. Any paper forms will be kept in a locked cabinet in a locked office. Demographics and characteristics of the overall cohort will be tabulated using means and standard deviations or counts and percentages, as appropriate. Prior to analysis, continuous measures will be tested for normality. Non-normally distributed variables will be transformed prior to analysis or non-parametric approaches will be utilized. Linear regression will be used to control for anthropometrics and other factors that may influence improvement and will contain no more than five predictors at a time, given our sample size of 40. Standardized mean differences and effect sizes with associated 95% CI will be calculated for outcomes of interest.

Training of study team:

As stated above all staff and soccer coaches will receive adequate training of all study procedures. All study staff and collaborators will take CITI training upon hire.

Confidentiality: Screens will be used on the soccer fields for consent and study measurements. All participants will receive a study ID and this will be used on all paper and electronic forms. We will destroy all identifiers and any audio from key interviews after the study is complete.

References

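### Two eligibility lists for the same 40 men set different lower and upper BMI limits, and nothing in the protocol says which list governs

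*Combined protocol and SAP*

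**What the plan says.** The protocol states BMI eligibility in three places.

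- **Research Design, Aim 2, Inclusion and Exclusion criteria:** BMI of at least 25 kg/m² to enter; BMI of 41 or more excluded.
- **Protection of Human Subjects, Human Subjects Involvement and Characteristics:** BMI of at least 27 kg/m² to enter, then "Exclusion criteria are participants with 1) T2DM diagnosis or medication; 2) BMI ≥ 33". This list is worded as a requirement, not as a description.
- **Specific Aims, paragraph after Aim 2b:** "BMI between 25 and 60".

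The Recruitment paragraph under Aim 2 provides for "confirmatory baseline assessments including BMI, blood pressure, HbA1c" and closes with "Participants meeting inclusion and exclusion criteria will be invited to participate in the study". It names no list.

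On the CDC score, the Specific Aims paragraph says "CDC pre-diabetes screening tool score >9", while the Aim 2 list says "CDC pre-diabetes risk score ≥ 9". The Protocol Synopsis and the Human Subjects list also use at least 9.

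Recruitment and Informed Consent gives the screening assumption for 70 men: "expect 30 screen fails for an enrollment of 40". The Data Analytics and Statistical Plan says "Demographics and characteristics of the overall cohort will be tabulated".

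**The concern.** BMI is checked for every man screened, and the result decides whether he enters the study. Outside the range where the lists agree, the protocol gives opposite answers: whichever decision staff take, one written criterion is breached. Staff working from different sections could decide differently about the same man.

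Two further things are at stake. First, someone reading the cohort tables would see the BMI values of the men enrolled but could not tell which population the study meant to recruit. Second, this is a feasibility study meant to inform later randomized trials, and its screening yield is hard to interpret if the entry rule is not fixed. The 30 expected screen failures are not tied to either list.

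**Working it through.** **1. Do the lists cover the same men?** Yes. The Aim 2 section describes a pilot in 40 men; the Human Subjects section describes recruiting 40 subjects for this study. The other numbered items match in substance: age 35 to 55, CDC score of at least 9, not currently active in soccer or a lifestyle programme, reading ability and consent, no type 2 diabetes diagnosis or medication, the 165/100 blood pressure limit, and no mobility problem or contraindication to high-intensity activity. BMI is the only material difference, so these are two copies of one list and not rules for two subgroups.

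**2. The plan's own figure.** 70 − 30 = 40, which reproduces the stated enrolment. The implied screen-failure share is 30/70 = 42.9%. No BMI limit enters this arithmetic.

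**3. The BMI ranges as intervals.**

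| Source | Admitted BMI | Width |
|---|---|---|
| Aim 2 criteria | 25 to <41 | 41 − 25 = 16 |
| Human Subjects list | 27 to <33 | 33 − 27 = 6 |
| Specific Aims text | 25 to 60 | 60 − 25 = 35 |

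**4. Where the two numbered lists disagree.**

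- Low end: 25 to <27, which is 27 − 25 = 2 units.
- High end: 33 to <41, which is 41 − 33 = 8 units.
- Total: 2 + 8 = 10 units; 10/16 = 62.5% of the wider range.
- Agreement that a man qualifies on BMI: 27 to <33 only.

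**5. The third range.** Its lower limit matches the Aim 2 list; its upper limit matches neither. The band from 41 to 60 (60 − 41 = 19 units) is admitted there and excluded by both lists, so the Specific Aims text does not settle which list applies.

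**6. Individual cases (BMI criterion only).**

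| BMI | Aim 2 | Human Subjects | Specific Aims |
|---|---|---|---|
| 26 | in | out | in |
| 30 | in | in | in |
| 35 | in | out | in |
| 45 | out | out | in |

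**7. CDC score.** More than 9 and at least 9 differ only for a man scoring exactly 9.

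**8. What cannot be computed.** The documents contain no BMI distribution for the target population, so neither the number of men affected nor the change in screen failures can be derived.

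**The case against.** The strongest reply is that context shows which list is meant. The sentence inviting men who meet the criteria ends the Recruitment paragraph that directly follows the Aim 2 lists, and most naturally refers to them. The Human Subjects section comes after the references and still treats ethics board permission as something to be sought, so it may be older text. This is a fair reading, but it is an inference. The Human Subjects list is worded as mandatory, nothing marks it as superseded, and the document has no amendment log or precedence clause. If one list is a leftover, that is the error, and the text does not show which one.

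Other points limit the concern and stand:

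- The screening forms are not in the documents, so inconsistent decisions are possible, not certain.
- The 62.5% is a share of BMI units and says nothing about how many men are affected.
- Height and weight are measured, so the BMI of the enrolled men can be reported; only the intended range is unclear.
- Screen failures can arise from any criterion, and the figure of 30 stands in the same part of the protocol as the narrower list, though it is not linked to it.
- The score mismatch is minor, with one sentence against three other places.
- In a single-arm pilot of 40, no power calculation or comparative test rests on BMI.

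None of this removes the contradiction between the two numbered lists.

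**Conclusion.** The concern holds. The two current eligibility lists for one cohort conflict on both BMI limits, and the rule cannot be followed for BMI 25 to <27 or 33 to <41 without breaching one of them: 10 of 16 units in the wider range. The ranges are nested, so a man with BMI 27 to <33 meets the BMI rule in all three places. The third range and the score wording are secondary.

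The conclusion rests only on the text and on treating both lists as current, which their presence in one dated version supports. It assumes nothing about how BMI is distributed. The consequence is confined to who is enrolled and how the target population is described. It still needs correcting, because the threshold decides enrolment.

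**What to change.** Reconcile the passages to one BMI range and one CDC score rule. Put identical wording in the Specific Aims, the Aim 2 criteria, the Human Subjects section and the screening forms, and align the Protocol Synopsis wording on the score. This review takes no position on which limits are right.

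As a smaller addition, state which criteria the 30 expected screen failures of 70 assume, and restate the figure if it was based on a different range.

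The cost is a short protocol amendment and aligned forms. The planned 40 men and the analysis do not change; the number to be screened may have to be restated.
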